## 12.0 SCHEDULE OF CLINICAL & LABORATORY EVALUATIONS

Prior to performing any study-specific procedures or evaluations, written informed consent and authorization for the use of protected health information (HIPAA) must be obtained in accordance with all applicable policies, regulations and laws.

Correlative evaluations must also be performed at specified visits. Please refer to Section 13.0 Correlative Studies for specific details.

### 12.1 Pre-Treatment Evaluation (Screening)

The following must be collected/ performed within  $\leq 28$  days prior to Cycle 1, day 1 of treatment. Clinical and laboratory evaluations performed as part of routine standard of care do not need to be repeated if performed within the appropriate window.

- Demographics: The age, race, ethnicity and gender of each patient
- Medical history: Relevant medical history including background and progress of the malignancy and description of all prior therapies
- Physical examination (PE): A complete PE will include assessments of general appearance, skin, head (eyes, ear, nose, and throat), neck, lungs, heart, abdomen, back, lymph nodes, extremities, and neurological exam
- ECOG Performance Status (ECOG PS) will be assessed as specified in Appendix C
- Height
- Weight
- Vital signs (V/S): Vital signs measurements include: diastolic blood pressure (BP) and systolic BP, heart rate (HR), respiratory rate (RR), oral temperature (oral temp) and oxygen saturation (O2)
- Complete Blood Count (CBC): CBC evaluations with differential and platelets
- Comprehensive Metabolic Panel (CMP): CMP evaluations to include magnesium, phosphate, and direct bilirubin
- Coagulation studies: PT/ (INR), aPTT
- Thyroid Function Tests (TFTs): Thyroid stimulating hormone (TSH), thyroxine (free T4), and triiodothyronine (T3)
- Urine pregnancy test: A pregnancy test will be performed for women of childbearing potential (WOCBP) at screening and throughout the study.
- Urinalysis: A urinalysis with microscopic analysis (UA micro) will be performed at Screening. Any patient with 1+ or greater protein screen without evidence of infection or contaminated sample must have urine microalbumin and/or 24 hour urine creatinine clearance to document proteinuria.
- 12-lead Electrocardiogram (ECG)
- 2D Echocardiogram (ECHO)
- Imaging studies for tumor assessment (CT and/or MRI of all known sites of disease): the same method of assessment and technique should be used at baseline and during treatment and follow-up
- Correlative studies:
  - PET/CT

- Tumor biopsy: Patients will require pre-treatment biopsy for tumor-infiltrating lymphocyte extraction and profiling as part of correlative studies. In the event that the pre-treatment biopsy is not adequate for immunohistochemistry testing, archival tissue may be substituted if deemed adequate by pathology for baseline staining. If the archival tissue dates prior to extensive chemotherapy/TKI therapy, or is not representative of the current tumor (i.e. primary lesion when the current disease is metastatic) then repeat biopsy should be attempted if feasible.
- Concomitant medications and procedures: Concomitant medications and procedures will be recorded beginning at the time of Screening
- Pretreatment events: baseline events, findings and conditions prior to study treatment initiation should be documented and continually reassessed throughout the study

## 12.2 Evaluations on Treatment

***Collection of Concomitant Medications should occur throughout trial treatment until 30-days ( $\pm 5$  days) post-treatment discontinuation.***

***The collection of Adverse Events (AEs) should occur throughout trial treatment and continue during Follow-up.*** Any SAE, or follow up to a SAE, including death due to any cause other than progression of the cancer under study that occurs to any subject from the time the consent is signed through **90 days** following end of treatment, or the initiation of new anti-cancer therapy, whichever is earlier, whether or not related to the Merck product, must be reported within 24 hours to the Sponsor and within 2 working days to Merck Global Safety. All subjects with SAEs must be followed up for outcome. (See Section 15.0 and Appendix A for details).

**Imaging studies should be done at the beginning of every odd cycle or 12 weeks (every 84 days  $\pm 7$  days) from the date of Registration/Enrollment, timed to coincide with the end of the prior treatment cycle; assessing all known sites of disease using the same type(s) of scan(s) that was/were performed at baseline.**

The appropriate axitinib dosing diary, blood pressure (BP) log monitoring forms and directions' sheet should be given to the patient before each treatment cycle (Appendix I). Afterwards, the dosing diary completed for that (previous) treatment cycle should be collected from the patient. This should be repeated for each cycle.

### 12.2.1 Cycle 1, day 1 ( $\pm 3$ days) – CTU visit

The following assessments should be performed on Cycle 1, day 1:

- PE
- ECOG PS
- V/S
- Weight
- CBC with differential

- CMP, Mg, Phosphate, direct bilirubin
- UA
- Urine pregnancy test (repeat only if not done within 7-days prior)
- Imaging studies (repeat only if screening imaging scans are deemed inadequate as per Radiology, i.e. missing fat suppression, contrast-enhancement, otherwise inadequate views, or performed outside of the 28 day window)
- Correlative studies: peripheral blood collection – see Section 13.0

12.2.2 Cycle 1, day 8 ( $\pm 3$  days) – CTU visit (Pembrolizumab administration)

The following assessments should be performed on Cycle 1, day 8:

- PE
- ECOG PS
- V/S
- Weight
- Patient dosing diary review and BP logs
- CBC with differential
- CMP, Mg, Phosphate, direct bilirubin
- Urine pregnancy test
- 12 lead EKG
- **Correlative studies: peripheral blood collection – see Section 13.0 (additional sample for expansion cohort)**

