**Table 2. Adequate Organ Function Laboratory Values.**

12. Age ≥ 16 years.
13. ECOG performance status of 0 or 1.
14. Patients must consent and be willing to undergo tumor core needle biopsies at three timepoints (1. baseline, 2. prior to starting Cycle 3, and 3. at off-study). At least one tumor site must be amenable to biopsy in the judgment of the interventional radiologist.
15. Female subject of childbearing potential should have a negative urine or serum pregnancy within 72 hours prior to receiving the first dose of study medication. If the urine test is positive or cannot be confirmed as negative, a serum pregnancy test will be required.
16. Females of child bearing potential that are sexually active must agree to either practice 2 medically accepted highly effective methods of contraception at the same time or abstain from heterosexual intercourse from the time of signing the informed consent through 120 days after the last dose of study drug. See Appendix G for

protocol-approved highly effective methods of contraceptive combinations. Subjects of childbearing potential are those who have not been surgically sterilized or have not been free from menses for > 1 year.

- a. Negative test for pregnancy is required of females of child-bearing potential; A female of child bearing potential is any woman, regardless of sexual orientation or whether they have undergone tubal ligation, who meets the following criteria:
    1. has not undergone a hysterectomy or bilateral oophorectomy; or
    2. has not been naturally postmenopausal for at least 24 consecutive months (i.e., has had menses at any time in the preceding 24 consecutive months or 730 days).
  - b. Conception while on treatment must be avoided
17. Male subjects should agree to use an adequate method of contraception starting with the first dose of study therapy through 120 days after the last dose of study therapy. Prior history of vasectomy does NOT replace requirement for contraceptive use.
  18. Suitable venous access to allow for all study related blood sampling
  19. Ability to understand and willingness to sign a written informed consent document.
  20. For minors that are 16 to 18 years of age, assent **and** parental (or legally acceptable representative) written informed consent must be obtained.

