12. Has known active central nervous system (CNS) metastases and/or carcinomatous meningitis or leptomenigeal disease. Subjects with previously treated brain metastases may participate provided they are stable (without evidence of progression by imaging for at least four weeks prior to the first dose of trial treatment and any neurologic symptoms have returned to baseline), have no evidence of new or enlarging brain metastases, and are not using steroids for at least 7 days prior to trial treatment. This exception does not include carcinomatous meningitis which is excluded regardless of clinical stability.
13. Concomitant (or receipt of) treatment with medications that may affect the metabolism of pembrolizumab and/or axitinib within 7 days prior to Cycle 1, day 1 of axitinib.
14. Has received a live vaccine within 30 days of planned start of study therapy. Note: Seasonal influenza vaccines for injection are generally inactivated flu vaccines and are allowed; however intranasal influenza vaccines (e.g., Flu-Mist®) are live attenuated vaccines, and are not allowed.
15. Is pregnant or breastfeeding, or expecting to conceive or father children within the projected duration of the trial, starting with the pre-screening or screening visit through 120 days after the last dose of trial treatment.
16. Any uncontrolled, intercurrent illness including but not limited to ongoing or active infection, symptomatic congestive heart failure, unstable angina pectoris, cardiac arrhythmia
17. Prolonged QTc interval on Screening EKG >475 ms.
18. Ejection Fraction <40% by 2D ECHO at Screening.
19. Any serious medical or psychiatric illness/condition including substance use disorders likely in the judgment of the Investigator(s) to interfere or limit compliance with study requirements/treatment.
20. Has active autoimmune disease that has required systemic treatment in the past 2 years (i.e. with use of disease modifying agents, corticosteroids or immunosuppressive drugs). Replacement therapy (eg., thyroxine, insulin, or physiologic corticosteroid replacement therapy for adrenal or pituitary insufficiency, etc.) is not considered a form of systemic treatment.

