## 6.0 ENROLLMENT PROCEDURES

To enter a patient, the Investigator or Study Team will contact the Clinical Research Services' (CRS) Representative. All eligibility requirements must be reviewed prior to the patient entering the study. The following information must be provided to the CRS Representative:

- 1) Completed and signed protocol-specific eligibility checklist;
- 2) All pages of the original signed informed consent form (ICF) including HIPAA Form B;
- 3) Relevant source documents including but limited to: subject medical history and physical exam, concomitant therapy, admission or discharge notes, diagnostic reports, pathologic confirmation of diagnosis, and relevant subject-specific written communication.

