**Study treatment must be initiated within seven (7) days of enrollment.**

## 7.0 STUDY DESIGN

The study will be a single-institution, open-label, single-arm phase II study. Since the primary endpoint is survival outcome (PFS) sample size calculation is based on a single-arm survival design. We will employ early stopping rules for lack of efficacy, based on previously reported historical controls (19% PFS at 3 months) and a large database suggesting that a progression-free rate at 3 months of >40% correlates with an active drug in the second-line setting for patients with advanced sarcoma (43). Patients will be treated with twice daily dosing of axitinib alone for the first 7 days, followed by concurrent axitinib administered twice daily at 5 mg PO twice daily, plus intravenous administration of pembrolizumab every 21 days (Figure 3). Patients will be assessed every three weeks for toxicity. After the first five patients are enrolled, we will assess safety of the combination. If 2 or fewer patients exhibit DLT, we will

then proceed with inpatient titration of axitinib dosing at each cycle based on the presence or absence of predefined toxicities (Section 7.1, Table 3). Correlative studies characterizing T-cells in tumor tissue and in peripheral blood will be performed at three timepoints: 1. pre-treatment, 2. on-treatment on cycle 3 day 1, and 3. off-study. Additional exploratory imaging investigations, and assessment of circulating tumor cells are included for all patients (See Appendix F for complete description of correlative studies).

**Figure 3. Schematic diagram of the study.** The first cycle of treatment will be seven weeks, with one week of axitinib alone prior to initiation of pembrolizumab. Subsequently, six-week cycles of treatment consist of twice daily oral doses of axitinib administered continuously with intravenous (I.V.) administration of pembrolizumab on day 1 and 22. The first five evaluable patients will be considered a safety lead-in, and will not have axitinib dose escalation above 5 mg PO bid. If 2 or fewer patients in the safety lead-in develop DLT, axitinib will then be individually titrated based on toxicity beginning on cycle 2 day 1.

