12.7 Calendar of Clinical and Laboratory Evaluations (continued on following page)

Cycle	Screening	1							2						3		Subsequent Cycles	Off Treatment (treatment discontinuation)	EoT Safety Evaluation	Follow-up A	Survival
		1	2	3	4	5	6	7	1	2	3	4	5	6	1	4 F					
Week (per Cycle)		1	2	3	4	5	6	7	1	2	3	4	5	6	1	4 F	Weeks 1 and 4 F,I,J	(EOT) ±7 days	30 days (±5 days) after EOT	Q12 Weeks (±7 days)	Q12 Weeks (±7 days)
Day (±3d per Cycle)	-28 to 0	1	8	15	22	29	36	43	1	8	15	22	29	36	1	22 F	Days 1 and 22 F				
ICF	X																				
Eligibility	X																				
Demographics	X																				
Medical history	X																				
PE	X	X	X	X	X	X	X	X	X	X	X	X	X	X	X		X (Day 1)	X	X	X	
ECOG PS	X	X	X	X	X	X	X	X	X	X	X	X	X	X	X		X (Day 1)	X	X	X	
Height	X																				
Weight	X	X	X	X	X	X	X	X	X	X	X	X	X	X	X		X (Day 1)	X	X	X	
V/S (BP, HR, RR, oral temp, and O 2 sat)	X	X	X	X	X	X	X	X	X	X	X	X	X	X	X		X (Day 1)	X	X	X	
CBC, diff	X	X	X	X	X	X	X	X	X	X	X	X	X	X	X	X	X (Days 1, 22)	X	X	X	

A For those patients without documented evidence of objective disease progression, the same imaging studies used at Baseline/Screening; not required at Off-Treatment, if reason for ‘off study’ is radiographic progression.

Cycle	Screening	1							2						3		Subsequent Cycles	Off Treatment (treatment discontinuation)	EoT Safety Evaluation	Follow-up A	Survival
		1	2	3	4	5	6	7	1	2	3	4	5	6	1	4 F					
Day (±3d per Cycle)	-28 to 0	1	8	15	22	29	36	43	1	8	15	22	29	36	1	22 F	Days 1 and 22 F				
CMP, Mg, PO4, direct bilirubin	X	X	X	X	X	X	X	X	X	X	X	X	X	X	X	X	X (Days 1, 22)	X	X	X	
PT/INR, aPTT	X								X						X		X (Day 1)	X	X	X	
TFTs (T3, T4, TSH)	X								X						X		X (Day 1)	X	X	X	
Urine pregnancy	X	X B	X			X			X			X			X	X	X (Days 1 and 22)	X	X	X	
U/A (micro-albumin and Cr Clearance, if > 2+ protein without other cause)	X	X							X						X		X (Day 1)	X	X	X	
12-Lead ECG	X		X			X						X C				(X) C	X C (Day 22 C )	X			
2D ECHO	X																	X			

B Repeat only if not done within previous 7 days.

C Perform only if axitinib dose escalation performed on day 1 of current cycle.

Cycle	Screening	1							2						3		Subsequent Cycles	Off Treatment (treatment discontinuation)	EoT Safety Evaluation	Follow-up A	Survival
		1	2	3	4	5	6	7	1	2	3	4	5	6	1	4 F					

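### The Cycle 1 day 1 schedule accepts a pregnancy test up to 7 days old, while inclusion criterion 15 calls for one within 72 hours of first dose

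*Combined protocol and SAP*

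**What the plan says.** Inclusion criterion 15 appears in the same terms in the Synopsis and in Section 5.1: a woman of childbearing potential "should have a negative urine or serum pregnancy within 72 hours prior to receiving the first dose of study medication". The first study medication is axitinib on Cycle 1 day 1, because Section 7.0 gives axitinib alone for the first 7 days.

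The visit schedule uses a different window. Section 12.2.1, listing the Cycle 1 day 1 assessments, has "Urine pregnancy test (repeat only if not done within 7-days prior". In the Section 12.7 calendar, footnote B on the day 1 urine pregnancy cell reads "Repeat only if not done within previous 7 days".

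Three other provisions affect timing:

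- Section 12.1 places screening procedures in the 28 days before day 1 and says "A pregnancy test will be performed for women of childbearing potential (WOCBP) at screening and throughout the study". It sets no 72-hour limit.
- Section 6.0 says "All eligibility requirements must be reviewed prior to the patient entering the study".
- The closing line of Section 6.3 says "Study treatment must be initiated within seven (7) days of enrollment".

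Criterion 16a also requires a negative test but gives no time window. Exclusion criterion 15 rules out a patient who "Is pregnant or breastfeeding, or expecting to conceive or father children within the projected duration of the trial".

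**The concern.** The eligibility list and the visit schedule give different limits for the age of the same test before the same dose. Staff working from Section 12.2.1 or the calendar are told not to repeat a test that criterion 15 treats as out of date. A woman can then start axitinib on schedule without meeting a listed inclusion criterion, and no procedure has been missed that would alert anyone.

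Two things are at stake. One is an unrecognised early pregnancy exposed to axitinib: a pregnancy not detectable when the older test was taken but detectable by day 1. The other is an eligibility deviation produced by following the schedule literally. The statistical design is not involved. Section 16.2 limits the analysis sets to study-eligible patients, but nothing in the text says that a late pregnancy test removes a woman from them.

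**Working it through.** The plan gives no figure to reproduce. The check compares the two windows and then follows the schedule forward from the first dose, taking day 1 as the day of that dose.

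**Inputs**

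| Item | Value | Source |
|---|---|---|
| Eligibility window | 72 hours before first dose | Criterion 15, Synopsis and Section 5.1 |
| Schedule waiver | 7 days before day 1 | Section 12.2.1; Section 12.7 footnote B |
| Enrolment to first dose | up to 7 days | Section 6.3, closing line |
| Next scheduled test | Cycle 1 day 8 ±3 days, no waiver | Section 12.2.2 |
| Axitinib dosing | twice daily from day 1 | Sections 7.0 and 8.3 |

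**Step 1: size of the mismatch.** The waiver is 7 × 24 = 168 hours. The difference is 168 − 72 = 96 hours, or 4 days. Any test age above 72 and up to 168 hours passes the schedule and misses criterion 15. For example, a test 5 days before dosing is 5 × 24 = 120 hours old, which lies inside that band.

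**Step 2: whether ordinary conduct reaches the band.** Suppose the test is done on the day of enrolment and axitinib starts *d* days later, with *d* at most 7. The test age at first dose is 24 × *d* hours:

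| *d* (days) | Test age (hours) | Schedule | Criterion 15 |
|---|---|---|---|
| 3 | 72 | no repeat | met |
| 4 | 96 | no repeat | not met |
| 5 | 120 | no repeat | not met |
| 6 | 144 | no repeat | not met |
| 7 | 168 | no repeat | not met |

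A test that was fresh when eligibility was reviewed can therefore be out of window at dosing, with every scheduling rule obeyed.

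**Step 3: exposure before the next test.** Day 8 ±3 runs from day 5 to day 11. Days of axitinib before retest are 5 − 1 = 4, 8 − 1 = 7 (nominal) or 11 − 1 = 10. At two doses a day without interruption, that is 8, 14 or 20 doses. The day 8 visit is also the first pembrolizumab visit and carries its own test, so the added exposure is to axitinib only.

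**Step 4: longest interval between consecutive tests.**

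- Under the waiver: 7 + 10 = 17 days (nominal 7 + 7 = 14).
- With 72 hours enforced: 3 + 10 = 13 days (nominal 3 + 7 = 10).
- Difference: 17 − 13 = 4 days, the same as 14 − 10.

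**The case against.** The strongest reply is that the two rules do different jobs and can both be met. Criterion 15 decides eligibility; Section 12.2.1 only says when a visit procedure need not be repeated, and it never says that a 7-day-old test makes a woman eligible. A site that tests in the last three days before dosing satisfies both, and Section 6.0 requires a signed eligibility checklist. This is fair, but the checklist is completed before entry and dosing may follow up to 7 days later, so no scheduled step secures 72 hours at the moment of dosing.

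The second reply is the wording: criterion 15 says *should*, while the firm requirement in 16a has no time window. That softens the point a little. However, the day 1 assessments are introduced with the same *should*, so the word does not rank one rule above the other.

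The third reply concerns size. The 8 to 20 doses before retest would be the same under the 72-hour rule, since the next test is at day 8 either way. What separates the rules is up to 4 days of test age. That is correct as a comparison of schedules. The dose count matters only for a woman whose pregnancy an in-window test would have caught: she would not have started, so those doses are her exposure.

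The protocol also gives no reason for choosing 72 hours and no test sensitivity by day, so the purpose attributed to the rule is an inference. And the safeguards are real: contraception or abstinence from consent (criterion 16), exclusion of pregnant women, a test at most 7 days old, and the day 8 retest. Fewer women may also remain to be enrolled, since Section 1.5 reports the first 30 patients accrued and plans up to 10 more; the documents do not say enrolment has closed. These points limit the consequence without reconciling the two windows.

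**Conclusion.** The inconsistency stands. Test ages above 72 and up to 168 hours pass the Cycle 1 day 1 schedule and miss criterion 15, and no other provision resolves the conflict. Relative to an enforced 72-hour window, the longest gap between tests grows by 4 days, from 13 to 17. A woman whose pregnancy would have shown on an in-window test could take 8 to 20 doses of axitinib before the next scheduled test.

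The dose range assumes uninterrupted twice-daily dosing and a day 8 visit kept within its window. The 17-day figure is the extreme: a test exactly 7 days old and a day 8 visit at +3 days. How many women would fall in the band cannot be estimated, because the documents give no distribution of test timing. It is a modest safety and eligibility-compliance defect that should be corrected, with no bearing on sample size, error rates or the planned estimates.

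**What to change.** In Section 12.2.1 and in footnote B of the Section 12.7 calendar, replace the 7-day waiver with an instruction to repeat the test on day 1 unless a negative result was obtained within 72 hours before the first dose. Add that the site confirms the result on the day of first dose, before axitinib is dispensed. Criterion 15 stays as written. The mismatch then falls from 96 hours to 0.

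The cost is one bullet, one footnote, and at most one additional urine test for some women at a visit they already attend.

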12.2.3 Cycle 1, day 15 ( $\pm 3$  days) – Clinic visit

The following assessments should be performed on Cycle 1, day 15:

- PE
- ECOG PS
- V/S
- Weight
- Patient dosing diary review and BP logs
- CBC with differential
- CMP, Mg, Phosphate, direct bilirubin

12.2.4 Cycle 1, day 22 ( $\pm 3$  days) – Labs only – may be done locally.

The following assessments should be performed on Cycle 1, day 22:

- Patient dosing diary and BP log review
- PE
- ECOG PS
- V/S
- Weight

- CBC with differential
- CMP, Mg, Phosphate, direct bilirubin

12.2.5 Cycle 1, day 29 ( $\pm 3$  days) – CTU visit – Pembrolizumab administration

The following assessments should be performed on Cycle 1, day 29:

- PE
- ECOG PS
- V/S
- Weight
- Patient dosing diary and BP log review
- CBC with differential
- CMP, Mg, Phosphate, direct bilirubin
- Urine pregnancy test
- 12 lead EKG

12.2.6 Cycle 1, day 36 ( $\pm 3$  days) – Labs only, locally permitted.

The following assessments should be performed on Cycle 1, day 36:

- PE
- ECOG PS
- V/S
- Weight
- Patient dosing diary and BP log review
- CBC with differential
- CMP, Mg, Phosphate, direct bilirubin

12.2.7 Cycle 1, day 43 ( $\pm 3$  days) – Labs only, locally permitted.

The following assessments should be performed on Cycle 1, day 43:

- Patient dosing diary and BP log review
- PE
- ECOG PS
- V/S
- Weight
- CBC with differential
- CMP, Mg, Phosphate, direct bilirubin

